6.3.4 Up-Dosing Interim (80 mg) Visit

The 80 mg in-clinic dosing visit is the approximate midpoint (approximately 10 weeks) of the Up-dosing Period. At this visit the following procedures are to be performed in addition to those performed at the other up-dosing visits (Section [6.3.3](#)):

- Complete physical examination, including height and weight
- For subjects with a clinical history of asthma, asthma assessment by clinical history and ACT ([Appendix 3](#))
- Urine pregnancy test for sexually active females of childbearing potential

6.3.5 End-Up-Dosing Phase Visit

The first 300 mg in-clinic dosing visit is the end of the Up-dosing Period. At this visit the following procedures are to be performed in addition to those performed at the up-dosing visits (Section [6.3.3](#)):

- Complete physical examination, including height and weight
- For subjects with a clinical history of asthma, asthma assessment by clinical history and ACT ([Appendix 3](#))
- Blood sample collection. Collect blood samples after measuring vital signs and PEFR and before administration of study treatment. These evaluations will serve as the exit visit screening/baseline values for the follow-on studies as applicable.
 - Peanut-specific IgE, total IgE, and peanut-specific IgG4 (immunoglobulin assays).
 - CBC, obtained with the same venipuncture as the blood draw for the immunoglobulin assays
 - Optional blood samples. Note that these samples can be obtained with the same venipuncture as the blood draw for the immunoglobulin assays and CBC, but will require an additional volume of blood to be collected. Separate informed consent is required.
- SPT to peanut extract
- Optional saliva collection ([Appendix 7](#))

6.3.6 Exit Visit/Early Discontinuation Visit

Subjects who tolerate their 300 mg dose for 2 weeks will have an Exit Visit per the SOE, and these evaluations will serve as the screening/baseline values for the follow-on studies as applicable. For subjects participating in follow-on studies, both follow-on protocols must be activated at the study site before subjects complete all of the required ARC007 study exit procedures. Certain procedures (specifically, completion of questionnaires and treatment unblinding) will be completed at a later unscheduled visit if necessary to accommodate IRB review of the follow-on protocols and shipment of open-label AR101. Additionally, all major data queries must be resolved before subjects complete exit procedures and proceed to a follow-on study. Blinded study treatment will continue to be dispensed to subjects until all exit requirements are met.

Subjects who fail initial escalation or up-dosing, or who prematurely discontinue treatment, will return to the site for an Early Discontinuation Visit that consists of the same procedures as the Exit Visit, except as noted below. An Early Discontinuation Visit is to occur 14 days after the last dose of IP. Subjects will return unused IP at this visit.

Subjects who withdraw from ARC007 wholly or in part due to intolerable GI symptoms, who are not enrolled in the optional saliva study, may be approached at the time of their Early Discontinuation Visit to provide voluntary consent to enroll and participate in the saliva sub-study. If this occurs, such subjects will provide a saliva sample as part of the Early Discontinuation Visit and then again during post-OIT follow-up ([Appendix 7](#)).

The following procedures will be performed at the Exit/Early Discontinuation Visit:

- Return unused capsules to the clinic
- Monitoring for compliance
- Concomitant medication review
- Complete physical examination, including weight and height
- Diet (food allergen) history
- Vital signs (BP, PR, body temperature)
- PEFR (3 attempts are to be performed). Airflow assessment should, as far as possible, be measured at the same time at each visit
- Urine pregnancy test for sexually active females of childbearing potential
- Optional saliva collection for those participating in the sub-study (at Early Discontinuation Visit only)
- Monitoring for AEs, including allergic symptoms (Section [7](#))
- Completion of the Total Nasal Symptom Score Sheet in subjects with allergic rhinitis
- Completion of the FAQLQ and the FAIM questionnaire after the completion of the exit procedures and unblinding
 - Treatment unblinding, FAQLQ, and FAIM will not be completed until both follow-on studies (ARC008 and ARC011) are activated at the study site, open-label AR101 is available, and all major queries are resolved. The subject will remain on blinded study treatment until all exit procedures are performed at a later unscheduled visit when all other conditions are met
- For subjects with a clinical history of asthma, asthma assessment by clinical history and ACT ([Appendix 3](#))
- Blood draw (at Early Discontinuation Visit and for subjects whose exit procedures are completed > 6 weeks after the 300 mg visit only) to collect samples for:
 - Peanut-specific IgE, total IgE, and peanut-specific IgG₄ measurement (immunoglobulin assays)
 - CBC, obtained with the same venipuncture as the blood draw for the immunoglobulin assays
 - Optional blood draw. Note that these can be obtained with the same venipuncture as the blood draw for the immunoglobulin assays. Separate informed consent is required.
- SPT to peanut extract

- Peanut allergy teaching refresher (as per Section 6.2)
- PEES v2.0 questionnaire (at Early Discontinuation Visit only)
- Dispense capsules for daily dosing until next unscheduled visit (only for subjects who must continue double-blind treatment until all exit requirements are met)

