3.4 Treatment Unblinding and Rollover to Studies ARC011 and ARC008

The treatment assignment for each subject will be unblinded after all exit visit procedures are completed and all major data queries for the subject have been resolved. For subjects participating in follow-on studies, both follow-on protocols must be activated at the study site before subjects can complete all of the exit procedures.

Subjects who received AR101 and completed ARC007 will have the option to participate in the ARC011 study. The ARC011 study is an open-label safety extension study of ARC007 to evaluate the safety and tolerability of 300 mg/d maintenance dosing for up to 6 months. After completing Study ARC011, subjects will be able to proceed to ARC008 for further maintenance dosing.

Subjects who received active treatment but did not reach 300 mg/d within 40 weeks or were unable to tolerate 300 mg daily for 2 weeks by 48 weeks after Day 1 will not be eligible for enrollment in ARC011 or ARC008.

Subjects who received placebo and completed ARC007 will be offered up-dosing and maintenance treatment with AR101 in the ARC008 study. In ARC008, these subjects will

undergo an escalation schedule identical to that for active subjects in the ARC007 study and then continue on maintenance dosing at 300 mg/d.

All subjects who enter ARC008 will be allowed to continue receiving AR101 until it becomes commercially available or the development program is terminated.

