6.2 Screening and Baseline

All screening procedures must be completed no later than 14 days from the signing of the informed consent and assent forms.

Screening will include the following assessments/procedures:

- Informed consent and assent, as age appropriate
- Inclusion/exclusion criteria review including obtaining and documenting medical records in source documents that support the history of reaction to known oral peanut exposure
- Medical, allergy, and dietary (food allergen exposure) history
- Completion of the FAQLQ and the FAIM questionnaire (prior to randomization)
- Asthma assessment by clinical history and ACT, for those subjects with a clinical history of asthma
- Concomitant medications
- Complete physical examination, including weight and height
- Vital signs (BP, pulse rate [PR], body temperature)

- Peak expiratory flow rate (PEFR) or spirometry (FEV₁)* (3 attempts are to be performed). Airflow assessment should as far as possible be measured at the same time at each visit.

*Note: Only for children 6 years of age and above and able to adequately perform spirometry. Spirometry is to be attempted in all subjects \geq 6 years of age. For subjects 6 to 11 years of age, if valid spirometry results are not successfully obtained, the attempt is to be documented. For subjects 4 or 5 years of age, peak flow rates are to be attempted, but reliable performance is not required for the subject to enter the study or undergo study procedures at the Investigator's discretion. The attempt must be documented, and a clinical assessment is required.

- Serum pregnancy test for sexually active females of childbearing potential
- Blood draw to collect samples for:
 - Peanut-specific IgE, total IgE, and peanut-specific IgG₄ assays. The amount of blood to be taken for the immunoglobulin assays will be communicated from the central laboratory and included in the manual of procedures.
 - Complete blood cell count (CBC), obtained with the same venipuncture as the blood draw for the immunoglobulin assays.
 - Additional blood samples for optional exploratory immunologic studies. Note that these samples can be obtained with the same venipuncture as the blood draw for the immunoglobulin assays and CBC, but will require an additional volume of blood to be collected. Separate informed consent is required.
- Optional collection of saliva sample for exploratory biomarker development (separate informed consent required)

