6.4 Unscheduled Visits / Unscheduled Blood Draws

The procedures performed at unscheduled visits may include any or all of those performed at up-dosing visits as well as PEES v2.0 questionnaire.

Subjects waiting for activation of follow-on protocols before completing their final exit visit procedures (treatment unblinding, FAQLQ, and FAIM) will continue blinded treatment and have an unscheduled visit every 4 weeks or sooner until all conditions are met for exiting the study. All exit visit procedures will be considered completed at the final unscheduled visit when unblinding, FAQLQ, and FAIM are completed. If the final unscheduled visit is more than 6 weeks after the scheduled exit visit, all exit visit procedures must be repeated. Additionally, laboratory evaluations must be repeated for subjects who exit the study > 6 weeks after the 300 mg visit, and these will serve as the screening/baseline values for the follow-on studies as applicable. Subjects will then enroll in the appropriate follow-on study based on their treatment assignment.

Additionally, if a subject or parent/guardian declares the intention to discontinue IP dosing, whether at a scheduled visit or an unscheduled visit, a blood draw should be performed to obtain a CBC, immunoglobulin assays, and optional blood and/or saliva samples (if the subject is participating in the sub-study). If a blood draw is performed at this time, it will take the place of the Exit Visit/Early Discontinuation Visit blood draw (Section 6.3.6).

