9. STATISTICAL CONSIDERATIONS

This protocol outlines the major statistical considerations for the ARC007 study. Full details on the statistical methodology to be used in the analysis and data handling for this trial will be described in the statistical analysis plan (SAP) to be developed prior to database lock and statistical analysis.

Data will be summarized using descriptive statistics within treatment group. No specific hypothesis testing or comparisons between the treatment groups are planned for this study.

Details of within-group comparisons relative to baseline values and any exploratory comparisons between groups will be described in the SAP.

Descriptive statistics will be presented in the following manner:

- Continuous data (ie, age, body weight, and height) will be summarized descriptively by mean, standard deviation, median, and range.
- Categorical data (ie, sex and race) will be presented as enumerations and percentages.

Data will be summarized by treatment group and treatment phase.

Data will be summarized in tables for each treatment group, treatment groups combined, and treatment phase.

Data will be listed for each subject.

The end of study is defined as the date of the last visit of the last subject.

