Appendix 1: Schedule of Events for ARC007

Visit	Screening/ Baseline	Initial Escalation		Up-dosing Period			Exit Visit	Early Discontinuation Visit ^b	Unscheduled Visit ^c
		Day 1	Day 2	CRC Dosing	Interim (80 mg) Visit	300 mg Visit			
Timing	Day 1 within 21 days after Consent/Assent			~Every 2 weeks for 20 to 40 weeks	Approximately Week 10	≤ Week 40 ^a	14 days after 300 mg Visit ^c	14 days after last IP dose	As needed
Informed consent & assent	X								
Inclusion & exclusion criteria	X								
Medical & allergy history	X								
Diet (food allergen) history	X	X		X	X	X	X	X	
Concomitant medications	X	X	X	X	X	X	X	X	
Physical exam ^d	X	X	X	X	X	X	X	X	
Vital signs (BP, PR, temp)	X	X ^e	X ^e	X	X	X	X	X	X
PEFR ^f	X ^g	X	X	X	X	X	X	X	X
Pregnancy test ^h	Serum			Urine			Urine	Urine	Urine
Blood draw	Total IgE & peanut-specific immunoglobulins	X				X ⁱ		X	X ^j
	CBC	X				X ⁱ		X	X ^j
	Optional blood sample(s) ^k	X				X ⁱ		X	X ^j
Saliva collection, optional ^k	X			X		X		X ^l	X
Skin prick test (food). Perennial, seasonal allergens at screening only	X					X	X	X	X
ACT	X				X	X	X	X	X
Peanut allergy teaching	X	X	X	X	X	X	X	X	X
FAQLQ & FAIM questionnaire	X						X ^c	X	X ^c
Total Nasal Symptom Score ^m	X	X		X	X	X	X	X	X
Monitor AEs/allergic symptoms	X	X	X	X	X	X	X	X	X
Randomization in IXRS		X							
Administration of IP at site		X	X	X	X	X			X
Dispense/return unused IP			X	X	X	X	X	X	X
Telephone follow-up ⁿ			X	X	X	X			X
Monitor for compliance				X	X	X	X	X	X
PEESS v2.0 questionnaire ^o							X	X	X

Abbreviations: ACT = Asthma Control Test; AE = adverse event; BP = blood pressure; CBC = complete blood cell count; CODIT = characterized oral desensitization immunotherapy; CRC = clinical research center; FAIM = food allergy independent measure (questionnaire); FAQLQ = food allergy related quality of life questionnaire; FEV₁ = forced expiratory volume in 1 second; IP = investigational product; GI = gastrointestinal; IXRS = interactive voice/web response system; PEESS = Pediatric Eosinophilic Esophagitis Symptom Score; PEFR = peak expiratory flow rate; PR = pulse rate; temp = body temperature.

- a) If the subject is unable to tolerate the 300 mg dose for the 2-week period after the End Up-dosing (300 mg) Visit, dosing may continue up to a maximum of 48 weeks after Day 1 to ensure tolerability prior to exiting the study.

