### 4.3 Exploratory Endpoints

The exploratory endpoints are as follows:

- Change in peanut-specific and peanut component-specific serum immunoglobulin (Ig) E and IgG4 levels
- Changes in peanut skin prick test (SPT) mean wheal diameter
- Changes in Total Nasal Symptom Score (TNSS) in subjects with allergic rhinitis

- Changes in scores of the Food Allergy Quality of Life Questionnaire (FAQLQ) and Food Allergy Independent Measure (FAIM)

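### Protocol 6.3.6 places the exit FAQLQ and FAIM after unblinding, and the SAP's by-arm change-from-baseline tables carry no note of it

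*Protocol*

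**What the plan says.** At screening, Protocol 6.2 lists "Completion of the FAQLQ and the FAIM questionnaire (prior to randomization"), so no family can know its assignment when it answers the baseline forms. At exit, Protocol 6.3.6 lists "Completion of the FAQLQ and the FAIM questionnaire after the completion of the exit procedures and unblinding".

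Two other sections bear on the order. Protocol 3.4 states: "The treatment assignment for each subject will be unblinded after all exit visit procedures are completed". Protocol 6.4, on subjects waiting for a follow-on study to open, states: "All exit visit procedures will be considered completed at the final unscheduled visit when unblinding, FAQLQ, and FAIM are completed". Section 6.3.6 also ties the two events together when exit is delayed: "Certain procedures (specifically, completion of questionnaires and treatment unblinding) will be completed at a later unscheduled visit".

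SAP 4.3 lists as an exploratory endpoint "Changes in scores of the Food Allergy Quality of Life Questionnaire (FAQLQ) and Food Allergy Independent Measure (FAIM"). SAP 9.8.12 says the instruments are given at baseline and at exit. It summarizes FAQLQ domain and total scores, and FAIM item and total scores, each with change from baseline, by age group and by who answered. In that section treatment group appears only as a sort key for listings. The AR101 and placebo columns come from the general convention in SAP 7.2, which covers all summary tables. Neither section mentions unblinding.

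In the Schedule of Events (Protocol Appendix 1), the row "FAQLQ & FAIM questionnaire" is marked at Early Discontinuation as well as at Screening and Exit. SAP 9.8.12 does not mention Early Discontinuation.

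**The concern.** Both instruments record perception. The FAQLQ domains include emotional impact, food anxiety and the risk of accidental exposure. The FAIM asks about expected outcome and perceived severity. A child or parent who has just been told that the past months were on AR101, or on placebo, may answer such questions differently from one who does not know. The same disclosure also tells the family whether the next step is maintenance in ARC011 or a first course of AR101 in ARC008.

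The study is offered as a source of placebo-controlled observations. Someone who meets AR101 and placebo columns of change scores in its report will take them to be blinded unless told otherwise. At stake is the reading of one exploratory endpoint.

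**Working it through.** No arithmetic applies. The documents give no standard deviation, expected change, error rate or power for either questionnaire, and no count of delayed exits. The check is a comparison of text.

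**1. Order at each end of the change score.** Baseline is before randomization (6.2) and exit is after unblinding (6.3.6). As 6.3.6 directs, each baseline-to-exit change pairs an answer given without knowledge of assignment with one given in full knowledge.

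**2. Is the order the same elsewhere?** Section 3.4 puts unblinding after all exit visit procedures. Section 6.3.6 lists the two questionnaires among the procedures of that visit but places them after unblinding. Section 6.4 counts unblinding itself, along with both questionnaires, among the things that complete the exit procedures, and gives no order. Read literally, 3.4 would have the forms done first and 6.3.6 would have them done last. Section 3.4 cannot be applied to the letter alongside 6.4, because unblinding cannot follow a set that includes itself. Only 6.3.6 sets the forms against unblinding explicitly, but the wording across the three sections is inconsistent.

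**3. Is the instruction general?** No. The ACT and the Total Nasal Symptom Score are also reported by subjects or parents and are listed for the same visit in 6.3.6, without any instruction to wait for unblinding. The documents give no reason for treating the FAQLQ and FAIM differently.

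**4. What the tables would show.** Write the mean change in arm *a* as T*a* + K*a*, where T*a* is the change that would be reported without disclosure and K*a* is the shift caused by learning the assignment. The difference between columns is then

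(T_AR101 − T_placebo) + (K_AR101 − K_placebo).

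Subtracting baseline does not remove the second bracket, because baseline precedes disclosure in both arms. It vanishes only if learning AR101 and learning placebo shift the answers equally. The documents give no basis for assuming that, and none for putting a value or a sign on the bracket.

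**5. Reach.** SAP 4.3 lists four exploratory endpoints, and one is affected. SAP 4.2 lists nine secondary endpoints and SAP 4.1 one primary endpoint. None of these uses the FAQLQ or FAIM.

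**6. Early Discontinuation.** Appendix 1 collects the forms there, but SAP 9.8.12 plans summaries for baseline and exit only. As the SAP stands, those forms appear in listings and in no named summary.

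**The case against.** The strongest reply is that no comparison is planned. Protocol Section 9 says "No specific hypothesis testing or comparisons between the treatment groups are planned for this study", the endpoint is exploratory, and the SAP plans no efficacy analysis. This stands as a limit on severity. It does not remove the problem, since change scores set in adjacent arm columns invite the comparison even when no test is run.

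Second, SAP Section 2 refers the reader to Protocol Sections 3 and 6 for procedures, so the timing can be found. That is fair. What is missing is a note where the numbers are read.

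Third, the order might be deliberate. Section 6.3.6 says exit evaluations serve as screening or baseline values for the follow-on studies where applicable, and ARC011 is open-label. The documents do not say that any follow-on study needs a questionnaire baseline taken after disclosure. Forms completed just before disclosure at the same visit could still serve as exit evaluations.

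Fourth, dosing reactions are frequent and expected (Protocol 7.2), so some families may guess their assignment before exit, and reordering would not give a perfectly blinded contrast. This stands. Reordering removes the effect of being told, not the effect of guessing.

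Fifth, the SAP is partly written in the past tense, and SAP 7.1 records subjects who had already stayed on treatment while waiting to roll over. A protocol change may therefore come too late for many subjects. This also stands, and it makes the SAP label the more practical part of the remedy.

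**Conclusion.** The point holds and is minor. As 6.3.6 directs, the exit FAQLQ and FAIM are answered with assignment known. The tables produced under SAP 9.8.12 and 7.2 show change from baseline by arm without saying so, and the protocol's own sections are not consistent on the order. The size of the bias cannot be derived. The conclusion assumes that sites follow 6.3.6 and that learning the assignment can shift answers about perceived risk and severity by different amounts in the two arms.

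Three stronger readings are tempting and not supported:

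- *The trial's blind, or its safety results, are compromised.* The instruction names only these two questionnaires. SAP Section 10 requires major queries, including those on severity and relatedness of adverse events, to be resolved before a subject is unblinded.
- *Sites used different orders.* The wording of 3.4 and 6.4 makes this possible, but nothing in the documents shows that it happened.
- *Forms from delayed exits will drop out of the tables*, because SAP 7.2 keeps unscheduled visits out of by-visit summaries. Protocol 6.4 treats the final unscheduled visit as completing exit, and the documents do not say under which visit label the forms are stored. This is missing detail, not a demonstrated loss of data.

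**What to change.** 1. Amend Protocol 6.3.6 so that the FAQLQ and FAIM are completed immediately before the assignment is disclosed, at whichever visit disclosure occurs. Align the wording of 3.4 and 6.4 with it. Keep the existing deferral of both forms and unblinding to the rollover point.
2. In SAP 9.8.12 and in the table footnotes, label scores already obtained in the 6.3.6 order as *collected after unblinding*, and state that the AR101 and placebo columns are not a blinded contrast.
3. Add the Early Discontinuation FAQLQ and FAIM scores to the SAP 9.8.12 summaries.

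The cost is a change of order within one visit and a few sentences in the SAP, with no extra visit or form. The protocol change needs the usual sponsor and IRB/EC approval (Protocol 10.1) and helps only subjects who have not yet exited. For the rest, items 2 and 3 are all that can be done. If a follow-on study does need a questionnaire baseline taken after disclosure, it would have to collect its own.
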